Appendix A

Clinical categories of chronic limb ischemia*

Grade 0	Category 0	Clinical description Asymptomatic – no hemodynamically significant occlusive disease	Objective criteria Normal treadmill or reactive hyperemia test
	1	Mild claudication	Completes treadmill exercise ¹ ; after exercise >50 mm Hg but at least 20 mm Hg lower than resting value
Ι	2	Moderate claudication	Between categories 1 and 3
II	3	Severe claudication	Cannot complete standard treadmill exercise ¹ and AP after exercise <50 mm Hg
II^2	4	Ischemic rest pain	Resting AP <40 mm Hg, flat or barely pulsatile ankle or metatarsal PVR; TP <30 mm Hg
III^2	5	Minor tissue loss – non healing ulcer, focal gangrene with diffuse pedal ischemia	Resting AP <60 mm Hg, ankle or metatarsal PVR flat or barely pulsatile; TP <40 mm Hg
	6	Major tissue loss – extending above TM level, functional foot no longer salvageable	Same as category 5

AP, Ankle pressure; PVR, pulse volume recording; TP, toe pressure; TM,

transmetatarsal.

Reference: Journal of Vascular Surgery. 1997;26(3).

¹ Five minutes at 2 mph on a 12% incline.

² Grades II and III, categories 4, 5, and 6, are embraced by the term chronic critical ischemia.

Appendix B

Hemodynamic Procedures

ABI and TBI Assessment

Explain the procedure and reassure the subject and ensure that he/she is lying flat and is comfortable, relaxed and rested with no pressure on the proximal vessels. Laying the subject supine reduces hydrostatic pressure inaccuracies. Reliability and ability to reproduce results both over time and between observers was tested and the index was found to vary by 0.06, considered acceptable. Measuring the pressure in both arms and using the higher of the two pressures increases the non- invasive accuracy of measurement of central systolic pressure but will not eliminate this potential limitation to the method

Measure the brachial systolic blood pressure:

- 1. Place an appropriately sized cuff around the upper arm
- 2. Locate the brachial pulse and apply ultrasound contact gel
- 3. Angle the Doppler probe at 45 degrees and move the probe to obtain the best signal
- 4. Inflate the cuff until the signal is abolished then deflate the cuff slowly and record the pressure at which the signal returns being careful not to move the probe from the line of the artery
- 5. Repeat the procedure for the other arm
- 6. Use the higher of the two values to calculate the ABPI.

Measure the ankle systolic pressure:

- 1. Place an appropriately sized cuff around the ankle immediately above the malleoli having first protected any ulcer that may be present
- 2. Examine the foot, locating the dorsalis pedis or anterior tibial pulse and apply contact
- 3. Continue as for the brachial pressure, recording this pressure in the same way
- 4. Repeat this for the posterior tibial arteries
- 5. Use the highest reading obtained to calculate the ABPI for that leg
- 6. Repeat for the other leg (At the screening visit only. The index leg will be used for future measurements).

Measure the toe systolic pressure:

- 1. Place an appropriately sized cuff around the hallux (1" toe) having first protected any ulcer that may be present. If the 1st toe is unavailable you may use other toes if appropriate
- 2. Examine the toe with the Doppler or photoplethysmograph (PPG), locating the pulse and apply contact
 - Note: The same method (Doppler or PPG) must be used on the patient for all assessments through study completion.
- 3. Continue as for the ankle pressure, recording this pressure in the same way
- 4. Repeat this for the other toe artery
- 5. Use the highest reading obtained to calculate the TBI for that leg
- 6. Repeat ABI and TBI for the other leg

Calculate the ABI and TBI for each leg using the formula below:

ABI = Highest Ankle systolic pressure/ Highest Brachial systolic

TBI = Highest Toe systolic pressure/ Highest Brachial systolic

Problems and errors may arise if:

- 1. The cuff is repeatedly inflated or inflated for long periods. This can cause the ankle pressure to fall
- 2. The cuff is not placed at the ankle
- 3. Ankle systolic pressure is not measured, pressure recorded is usually higher than ankle pressure
- 4. The pulse is irregular or the cuff is deflated too rapidly
- 5. The true systolic pressure may be missed and inappropriately high reading will be obtained, if the vessels are calcified (associated with diabetes), the legs are large, fatty or edematous, the cuff size is too small, or the legs are dependent,
- 6. Central systolic pressure may influence the 'normal' range for the ABPI

Appendix C

The Visual Analog Scale (VAS) Procedures

Pain Intensity Rating using a Visual Analog Scale (VAS)

The visual analog scale (VAS) is a 10-cm line, oriented horizontally, with one end indicating "no pain" and the other end representing "pain as bad as it can be".

- 1. The subject is asked to mark a place on the line corresponding to the current pain intensity.
- 2. The distance along the scale is then converted into a numeric reading by measuring the distance of the subjects mark in centimeters from the beginning of the scale (the 0 mark).
- 3. The CRF will be faxed into DataFax and the measurement will be electronically recorded in the database

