4.1.1 Primary Safety Endpoints

The primary safety endpoints include the following:

- 1. Incidence of adverse events through Day 365.
- 2. Change from Baseline in clinical chemistry, hematology, u/a at Days 15, 28, 59, 91, 180 and 365.
- 3. Injection site reactions, as measured by assessments at Days 1, 8, 15, 21, 28, and 59 using National Cancer Institute's Common Terminology for Adverse Events v3.0 criteria as follows:

Grade 1=Pain, itching, erythema;

Grade 2=Pain or swelling with inflammation or phlebitis;

Grade 3=Ulceration or necrosis that is severe or operative intervention indicated.

4. Clinically significant changes in physical examination from Baseline at Days 15, 28, 59, 91, 180 and 365.

Secondary Efficacy Endpoints

The Secondary Efficacy endpoints include the following:

- 1. Change from Baseline in hemodynamic measurements (Appendix B: ABI, TBI, and Wave Form Analysis) and TcPO₂ at Days 15, 28, 59, 91, 180 and 365.
- 2. Change from Baseline in subject-assessed pain, as measured by the VAS (Appendix C) at Days 15, 28, 59, 91, 180 and 365.
- 3. Change from Baseline in ulcer area, in square millimeters, as assessed by digital photograph and measurement of the largest contiguous ulcerated area, at Days 15, 28, 59, 91, 180 and 365.

Pharmacokinetic Evaluations

Pharmacokinetics of VM202 will be assessed using blood VM202 DNA concentration levels from samples obtained pre-dose at the first dose administration (Day 1). In addition, levels will be measured at Days 21, and 59 (if DNA is detected at Day 21).

Pharmacodynamic Evaluations

Pharmacodynamics will be assessed as the change from Day 1 in serum HGF level at Days 8, 15, 21 and 59. Potential immune response to HGF will be assessed as change

from Day 1 in level of neutralizing antibodies (anti-HGF antibodies) at Days 15, 28, 59 and 180. The ability of HGF to stimulate cell growth will be assessed as the change from Baseline in level of endothelial progenitor cell assay at Days 15, 28, 59 and 180.

Overall Study Design

The overall trial design includes: 1) a multi-dose Phase I safety and tolerability evaluation; 2) a preliminary efficacy, pharmacokinetic and pharmacodynamic evaluation; and 3) a safety review between dosing cohorts in order to meet defined safety criteria. The study will evaluate vascular assessments as primary measures of efficacy and adverse event collection and laboratory parameters as the primary monitored measures of safety (see Table 4-1).

Study Population

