7.1.2 Physical Examination

The Investigator will perform a full physical examination at Baseline and at Days 15, 28, 59, 91, 180 and 365. All changes from the Baseline will be documented on the CRF pages at the time of the follow-up physical examination.

7 1 2 1 Assessment of CLI

The lower extremities will be examined specifically for clinical evidence of CLI, such as ischemic rest pain, ischemic ulceration, gangrenous skin changes, or residual open wound(s) from minor amputation.

Subjects will be classified as having ischemic rest pain if the pain required analysis for more than 2 weeks, and includes the following clinical characteristics:

- 1. Persistent or recurrent pain of the distal portion of the leg (usually toes, forefoot or ankle),
- 2. Pain begins or is increased, on elevation of the leg and improved by dependency.

Ischemic ulceration and gangrenous skin changes are equivalent necrotizing processes for the purpose of this study. In the case of residual open wound(s) from minor amputation, these will be considered ulceration(s) for the purposes of this assessment.

The Investigator will assess the number of individual ulcers and/or gangrenous tissue site(s) for location and size. Excess necrotic tissue and eschar will be removed when possible before taking measurements. Photographs of each ulceration/gangrene area will be taken for documentation purposes only. Two photographs of each ulceration/gangrene area will be obtained at each efficacy time point regardless of whether the area still contains the ulcer/gangrene, and regardless of how many doses of test material the subject received. During the monitoring visit, the monitor will retrieve one of the two photographs for each ulceration/gangrene area. The border of all photographs will be labeled with the photograph date, subject's initials, and the subject's study number assignment.

On efficacy assessment visits, the ulceration/gangrene area will be considered completely healed if assessed as having complete skin closure without drainage or dressing requirements. An ulceration/gangrene area that heals but re-appears and is unhealed at the assessment will be considered not healed. If the subject is discontinued from treatment, he/she will continue to be followed for ulceration/gangrene evaluations so that the subject's data can be included in analyses. If the subject is lost to follow-up without a proper ulceration/gangrene evaluation, the subject will be considered not to have healed.

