7.2.2 High Resolution MRA

Subjects will have High Resolution MRA at Baseline and at 3 months and 6 months post-treatment. Area of Ischemic Ulcer (Digital Photography and Ulcer Measurement)

If one or more ischemic ulcer is present on the subject's studied limb, a digital photograph will be taken of the largest contiguous area of ulceration with a target plate included in the image for calibration purposes. The wound perimeter will be traced and the area of ulceration will be calculated in square millimeters. If a MRA can not be done, a CT-Angio (CTA) can be performed on the subject.

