7.2.3 Pain VAS Score

Pain intensity will be assessed by subjects marking a place on a 100 mm visual analog scale ranging from 0=no pain to 100=worst possible pain as described in Appendix C. The distance from 0 to the mark will be measured in millimeters (0 to 100) and recorded on the CRF as the VAS score.

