Viromed Co., Ltd. Protocol Number: US-06-1-001

Table 5 Ulcer Measurement (cm²) [1] ITT Population

| | VM202- 2 | mg (N=) | VM202-4 | mg (N=) | VM202-8 | mg (N=) | VM202-10 | 5 mg (N=) |
|-------------------|--------------|--------------|--------------|--------------|--------------|--------------|--------------|--------------|
| | Result | Change [3] |
| Baseline [2] | | | | | | | | |
| N | n | | n | | n | | n | |
| Mean (SD) | xx.x (xx.xx) | | xx.x (xx.xx) | | xx.x (xx.xx) | | xx.x (xx.xx) | |
| Median | XX.X | | XX.X | | XX.X | | XX.X | |
| Min, Max | XX, XX | | xx, xx | | XX, XX | | xx, xx | |
| Day 15 (Pre-Dose) | | | | | | | | |
| Ň | n | n | n | n | n | n | n | n |
| Mean (SD) | xx.x (xx.xx) |
| Median | xx.x |
| Min, Max | XX, XX |
| Day 28 | | | | | | | | |
| Ň | n | n | n | n | n | n | n | n |
| Mean (SD) | xx.x (xx.xx) |
| Median | xx.x |
| Min, Max | XX, XX |
| Day 59 | | | | | | | | |
| Ň | n | n | n | n | n | n | n | n |
| Mean (SD) | xx.x (xx.xx) |
| Median | xx.x |
| Min, Max | XX, XX |
| | | | | | | | | |

path\t_program.sas date time

Programmer Note Repeat for all available time points.

^[1] Measurement taken was the largest contiguous area of ulceration.[2] Baseline defined as measurement taken most closely prior to first study drug administration.

^[3] Change= Change from Baseline

Viromed Co., Ltd. Page 1 of x Protocol Number: US-06-1-001

> Table 6 Ankle Brachial-Index (mmHg) ITT Population

| | VM202- 2 | mg (N=) | VM202-4 | mg (N=) | VM202-8 | mg (N=) | VM202-10 | 6 mg (N=) |
|-------------------|--------------|--------------|--------------|--------------|--------------|--------------|--------------|--------------|
| | Result | Change [2] |
| Index Limb | | | | | | | | |
| Right | n (%) | | n (%) | | n (%) | | n (%) | |
| Left | n (%) | | n (%) | | n (%) | | n (%) | |
| Delt | П (70) | | 11 (70) | | 11 (70) | | 11 (70) | |
| ABI Index Leg | | | | | | | | |
| Baseline [1] | | | | | | | | |
| N | n | | n | | n | | n | |
| Mean (SD) | xx.x (xx.xx) | | xx.x (xx.xx) | | xx.x (xx.xx) | | xx.x (xx.xx) | |
| Median | XX.X | | XX.X | | XX.X | | XX.X | |
| Min, Max | XX, XX | | XX, XX | | XX, XX | | XX, XX | |
| , | , | | , | | , | | , | |
| Day 15 (Pre-Dose) | | | | | | | | |
| Ň | n | n | n | n | n | n | n | n |
| Mean (SD) | xx.x (xx.xx) |
| Median | xx.x |
| Min, Max | XX, XX |
| | | | | | | | | |
| | | | | | | | | |
| ABI Non-Index Leg | | | | | | | | |
| Baseline [1] | | | | | | | | |
| N | n | | n | | n | | n | |

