| Mean (SD) | xx.x (xx.xx) | | xx.x (xx.xx) | | xx.x (xx.xx) | | xx.x (xx.xx) | |
| Median | XX.X | | XX.X | | XX.X | | XX.X | |
| Min, Max | XX, XX | | XX, XX | | XX, XX | | XX, XX | |
| , | , | | , | | , | | , | |

^[1] Baseline defined as measurement taken most closely prior to first study drug administration.
[2] Change= Change from Baseline

Viromed Co., Ltd. Page 1 of x

Protocol Number: US-06-1-001

Table 7 Toe Brachial-Index (mmHg) ITT Population

| | VM202-2 | mg (N=) | VM202- 4 mg (N=) | | VM202-8 | mg (N=) | VM202-10 | 5 mg (N=) |
|-------------------|--------------|--------------|-------------------|--------------|--------------|--------------|--------------|--------------|
| | Result | Change [2] | Result | Change [2] | Result | Change [2] | Result | Change [2] |
| TBI Index Toe | | | | | | | | |
| Baseline [1] | | | | | | | | |
| N | n | | n | | n | | n | |
| Mean (SD) | xx.x (xx.xx) | | xx.x (xx.xx) | | xx.x (xx.xx) | | xx.x (xx.xx) | |
| Median | XX.X | | XX.X | | XX.X | | XX.X | |
| Min, Max | XX, XX | | xx, xx | | xx, xx | | XX, XX | |
| Day 15 (Pre-Dose) | | | | | | | | |
| N | n | n | n | n | n | n | n | n |
| Mean (SD) | xx.x (xx.xx) | xx.x (xx.xx) | xx.x (xx.xx) | xx.x (xx.xx) | xx.x (xx.xx) | xx.x (xx.xx) | xx.x (xx.xx) | xx.x (xx.xx) |
| Median | XX.X | XX.X | XX.X | XX.X | XX.X | XX.X | XX.X | XX.X |
| Min, Max | XX, XX | XX, XX | xx, xx | XX, XX | XX, XX | XX, XX | XX, XX | XX, XX |
| | | | | | | | | |
| TBI Non-Index Toe | | | | | | | | |
| Baseline [1] | | | | | | | | |
| N | n | | n | | n | | n | |
| Mean (SD) | xx.x (xx.xx) | | xx.x (xx.xx) | | xx.x (xx.xx) | | xx.x (xx.xx) | |
| Median | XX.X | | XX.X | | XX.X | | XX.X | |
| Min, Max | XX, XX | | xx, xx | | xx, xx | | xx, xx | |
| | | | | | | | | |

^[1] Baseline defined as measurement taken most closely prior to first study drug administration.

path\t_program.sas date time

Programmer Note For each measurement, repeat for all available time points.

^[2] Change= Change from Baseline

Table 8 Visual Analogue Scale for Pain (mm) ITT Population

| | VM202- 2 | mg (N=) | VM202-4 | mg (N=) | VM202-8 | mg (N=) | VM202-16 mg (N=) | |
|-------------------|--------------|--------------|--------------|--------------|--------------|--------------|-------------------|--------------|
| | Result | Change [2] | Result | Change [2] | Result | Change [2] | Result | Change [2] |
| Baseline [1] | | | | | | | | |
| N | n | | n | | n | | n | |

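### Appendix C has the pain VAS read in centimetres while section 7.2.3 and the SAP use millimetres, and SAP Table 5 heads ulcer area in cm² while the protocol defines it in mm²; no conversion is stated for either

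*Protocol*

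**What the plan says.** **Pain VAS.** Protocol section 7.2.3 has the subject mark a 100 mm line and then fixes the recorded value: "The distance from 0 to the mark will be measured in millimeters (0 to 100) and recorded on the CRF as the VAS score". Appendix C describes the same line as 10 cm long. Its step 2 turns the mark into a number by "measuring the distance of the subjects mark in centimeters from the beginning of the scale (the 0 mark". Step 3 sends the CRF through DataFax and names no unit. SAP section 9.3 uses a 0 to 100 scale, and Table 8 carries the title "Visual Analogue Scale for Pain (mm" with the unit in brackets. No multiplication by 10 appears in either document.

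**Ulcer area.** The secondary efficacy endpoint in protocol section 4.1 is "Change from Baseline in ulcer area, in square millimeters, as assessed by digital photograph". Section 7.2.2 asks for an image of the largest ulcer with a calibration plate, has the perimeter traced, and says "the area of ulceration will be calculated in square millimeters". SAP section 9.1 gives neither a unit nor a source for the value. The Table 5 layout is headed "Ulcer Measurement (cm²", again with the unit in brackets. No division by 100 is stated.

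**Photographs.** Protocol section 7.1.2.1, the assessment of CLI, says "Photographs of each ulceration/gangrene area will be taken for documentation purposes only".

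**The concern.** Step 2 of Appendix C is an operative instruction. Staff who follow it record 6.5 where staff who follow section 7.2.3 record 65. The SAP would then summarise both numbers as millimetres.

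If every reading were in centimetres, the scale would be mislabelled but relative changes would survive. If the unit differed between visits or subjects, change from baseline would show a false improvement or worsening. With three subjects per cohort, one such value dominates a mean.

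The VAS is the tool named for the first secondary objective, and ulcer area is a listed secondary endpoint. Ulcer area carries a similar labelling risk, but between the protocol and one SAP table heading rather than within the measurement instructions.

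**Working it through.** The plan has no figure of its own to reproduce here. The check is unit arithmetic plus a comparison of the texts.

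**1. Conversion factors.**
- Length: 10 cm = 100 mm, so a centimetre reading treated as millimetres is too small by a factor of 100/10 = 10.
- Area: 1 cm² = 10 × 10 = 100 mm², so a mm² value printed under a cm² heading is overstated 100-fold. An area of 400 mm² is 4 cm²; unconverted, it would appear as 400 cm².

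**2. Which VAS values are ambiguous.** A centimetre reading on a 10 cm line lies between 0 and 10. A recorded value above 10 must therefore be in millimetres. A value of 10 or less is valid in either unit, so a range check cannot resolve it.

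**3. Effect of one mixed-unit VAS value (assumed scores, n = 3 per cohort).** Let the true scores be 65, 70 and 60 mm at both visits, with the first follow-up entered in centimetres as 6.5.
- Baseline mean: (65 + 70 + 60)/3 = 65.0.
- Follow-up mean: (6.5 + 70 + 60)/3 = 45.5.
- Mean change: 45.5 − 65.0 = −19.5 mm, and −19.5/65.0 = −30%.
- Individual changes: −58.5, 0, 0. Median change 0, minimum −58.5.

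If all three subjects share a true score v, the follow-up mean is (v + v + v/10)/3 = 0.7v, again −30%:

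| True score, all three (mm) | Mean with one value in cm | False change (mm) |
|---|---|---|
| 40 | 28 | −12 |
| 60 | 42 | −18 |
| 80 | 56 | −24 |

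**4. Effect on ulcer area.** If all values are in mm² under a cm² heading, the level is wrong 100-fold but the direction and percentage of every change are right. If one of three areas of 400 mm² were entered as 4, the mean would be (400 + 400 + 4)/3 = 268, a fall of 33%. Nothing in the documents says that units would be mixed in this way.

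**5. Side by side.** For the VAS, section 7.2.3, SAP section 9.3 and Table 8 agree on 0 to 100, in millimetres where a unit is given. The single outlier is the word *centimeters* in Appendix C, step 2. For ulcer area, protocol sections 4.1 and 7.2.2 agree on mm², and the outlier is the heading of SAP Table 5.

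**The case against.** The strongest reply is that the recording and analysis rules already agree. In section 7.2.3 the reference to Appendix C belongs to the sentence about marking the scale, and the next sentence independently fixes millimetres on the CRF. Table 5 is only an output layout, and rescaling mm² to cm² is routine. The plan also provides for program validation and senior statistical review (SAP section 4), monitoring of CRF entries and an audit of key efficacy data before lock (protocol sections 10.2.5 and 10.2.6), and a listing of VAS by subject (SAP Listing 11). Table 8 also reports median, minimum and maximum, so a change of −58.5 beside two zeros would be seen.

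Much of this stands. It limits the harm but does not remove the conflicting instruction. Validation against the plan cannot supply a conversion that the plan omits, and seeing an outlier does not establish its unit.

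Three stronger readings are tempting but unsupported:
- **That the photograph's role is contradicted, so the measuring method could switch between visits.** Section 7.1.2.1 concerns documentation photographs of every ulcer or gangrenous site, within the assessment of CLI (SAP Listing 9, CRF plate 17). Section 7.2.2 describes the calibrated, traced image of the largest ulcer (SAP Listing 7, CRF plate 16). A switch of method is speculation.
- **That the data can never reveal the VAS unit.** This is true only of values of 10 or less, and for those the marked line can be checked.
- **That 10-fold or 100-fold errors will occur.** They arise only if values go unconverted or units are mixed. The CRF, which may state the unit, is not among the documents.

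**Conclusion.** The point holds as two unit inconsistencies in the current text. Appendix C, step 2, is wrong as written: followed literally, it puts a 10-fold understatement into a table labelled in millimetres. The heading of SAP Table 5 departs from the protocol's unit without a conversion and would mislabel unconverted areas 100-fold.

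The factors 10 and 100 are exact. The 30% shift in a cohort mean rests on assumed scores and on one of three values being in the wrong unit.

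Severity is minor to moderate. Both measures are secondary, protocol section 9.1 plans no statistical analysis of efficacy, and SAP section 8 calls the efficacy analysis exploratory. A reader might infer a risk to the safety conclusions or to dose escalation. The documents do not support that, because neither the DLT definition nor the escalation rule uses these measures.

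**What to change.** 1. **Appendix C, step 2:** replace *centimeters* with *millimeters (0 to 100)*.
2. **Recorded VAS data:** check every value of 10 or less against the marked line on the retained CRF. Table 4-1 schedules eight VAS readings per subject (screening and Days 1, 15, 28, 59, 91, 180 and 365), so 12 to 15 subjects give at most 12 × 8 = 96 to 15 × 8 = 120 scheduled readings, and only the low ones need checking.
3. **SAP Table 5 and section 9.1:** head the table in mm², or keep cm² and state in section 9.1 that cm² = mm²/100.
4. **SAP section 9.1:** say that the analysed value is the area traced on the calibrated photograph under protocol section 7.2.2.
5. **Protocol section 7.1.2.1:** keep the sentence on documentation photographs, adding at most a cross-reference to section 7.2.2.

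The cost is a one-word correction in the appendix, a table heading or one line of conversion, a sentence in the SAP and a short source check. No new visits or measurements are needed, and no sample size or error rate changes.
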